Several lines of evidence demonstrate that ketones are a preferred fuel for the brain, have neuroprotective effects, and may enhance neurocognitive function in various pathological or physiologically stressed states. At the low end of nutritional ketosis (0.5 mM), ~5% of whole brain energy metabolism is provided by ketones. At ketone concentrations of 1.5 mM (typical of KDs), ketones supply nearly 20%; at the higher end of nutritional ketosis 4-5 mM [achievable with ketone esters (KE)], half of the brain energy demands are met by ketones [18-20]. Importantly in situations where brain glucose metabolism is impaired, uptake and utilization of ketones remain fully intact [21], suggesting a hierarchy of importance placed on ketones as the preferred fuel for human brains. For example, when ketones are elevated in the circulation there is a remarkable protection from the adverse signs of hypoglycemia [16, 17].

RESEARCH OBJECTIVE

• Determine the degree to which short-term use of ketone esters (KEs) protects against fatigue from moderate sleep restriction and exercise.

Key outcome variables will include **5** major categories:

1) SLEEP OUTCOMES

- a) The sleeping protocol will be monitored by investigators and personnel with experience in sleep medicine. Participants will be required to reduce sleep by 50% of normal, for 4 consecutive nights, to observe potential deficits in physical and cognitive performance [22].
- b) Heart rate and sleep parameters (timing, duration, and quality of sleep) will be assessed by wrist-based acceleration with cloud technology (Polar Unite[™], Polar USA). This monitor is less burdensome than other sleep monitoring technologies and less likely to interfere with normal sleep and activity demands of the cadets. We have used this watch in our work with athlete tracking in sport science with reliable and valid results. Each participant will be fitted with the watch for acclimatization and then establish 3-day baseline patterns for 3 nights before the sleep loss protocol.
- c) Dietary standardization, including the same meals for all subjects and control of caffeine, will be implemented. Proper hydration will also be emphasized and evaluated at testing sessions via urine specific gravity.

2) EXERCISE PERFORMANCE

- a) Since weight training is now a crucial part of any warfighter's physical preparation, we will have subjects perform two weight training workouts emphasizing all major muscle groups on Days 2, 3 and 4.

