- b) Workouts will be supervised by trained personnel. All physical activity will be performed in our laboratory weight room located in the Physical Activity and Educational Services (PAES) Building ([name]).
- c) On Days 1 and 5, cognitive and physical tests and questionnaires (McGill Pain Questionnaire, the Shortened Profile of Mood States, and the Pittsburgh Sleep Quality Index) will be examined around the sleep restriction/exercise challenge. Time of day, eating, and activity will be strictly standardized the day prior to all assessments.

3) NEUROPSYCHOLOGICAL ASSESSMENTS

a) The first cognitive assessment will be done via *Automated Neuropsychological Assessment Metrics* (**ANAM**) (Department of Defense, [name]). This cognitive battery is a library of computer-based tests of domains including attention, concentration, reaction time, memory, processing speed, decisionmaking, and executive function. The ANAM core testing battery will be used, which assess of the following areas: participant information, sleepiness scale, symptoms checklist, mood scale, simple reaction time, code substitution- learning, procedural reaction time, mathematical processing, matching to sample, code substitutiondelayed, simple reaction time (repeated), and go no go.

- b) The second cognitive assessment will be delivered via Cambridge Neuropsychological Test Automated Battery (CANTAB). This iPad delivery assessment will include an Information Sampling Task to test impulsivity and decision making, response time (in msec), which provides a level of sensitivity not available with traditional paper and pencil tasks, processing speed, executive functioning, and spatial memory. We have also incorporated tasks which assess the ability to rapidly identify expressed facial emotions, which may index one's ability to accurately respond to overtly threatening or non-threatening stimuli.

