Participants that meet the initial qualifying criteria will visit the study center for a screening meeting. The participant and a member of the research team will meet in a private office to discuss the informed consent form. The informed consent form will be provided to the participant for their review, the study will be described in full detail and any questions the interested participant has will be encouraged and responded to. If they choose to participate in the study, they will be asked to sign the consent form providing written consent. The participant will be informed that even though they signed the consent form, their participation in the study is dependent on the results of their questionnaires to determine if they meet the study criteria. If the participant provides consent, they will be provided with a few questionnaires including medical history, physical activity history, a menstrual history for women, a food frequency questionnaire, and a gastrointestinal health status questionnaire. All collected samples will be coded to maintain participant anonymity. We will also measure height, weight. Participants will receive a call from one of the study personnel within days of the screening visit to inform them if they are eligible or not and will provide the participants with their results from the screening visit. If the participant is eligible for the study and is still interested in participating, then he/she will be scheduled to return to the study center for baseline testing.

Testing Sessions.

A schedule of the testing battery for the 5-day sleep restriction protocol is provided in **Figure 2**. The familiarization meeting will describe all the protocols in greater detail to accustom participants to their study duties and minimize training learning effects, followed by 5, consecutive, in-person testing sessions. Days 1 and 5 comprise primarily of blood assessment, cognitive testing, virtual simulator shooting, and power/reaction time test. Days 2, 3, and 4.

	Blood Draw	HR Monitoring	CGM/CKM	Cognitive Tests	Surveys	VirTra	Power/RT
Familiarization		х	х	х	х	Х	х
Day 1	х	х	х	х	х	Х	х
Day 2		х	х				
Day 3		х	х				
Day 4		х	х				
Day 5	х	х	Х	Х	Х	х	Х

Table 1 | Experimental Checklist.

HR, heart rate; CGM/CKM, continuous glucose/ketone monitoring; VirTra, Virtual Training; RT, reaction time.

[figure not shown]

Figure 2 | Experimental Timeline During Sleep Deprivation Protocol.

Familiarization:

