- 7. *Force plate*: Whole body power will be assessed with a repetitive 10-jump test that we developed. Power (peak, average, curve functions) will be assessed using an AMTI force plate with Accupower 2.0 software (Advanced Mechanical Technology Inc, Watertown, MA).
- 8. *Response time*: Upper body and lower body reaction time will be measured using the Quick Board (The Quick Board, Memphis, TN). The Quick Board system is comprised of an iPad (Apple Inc., Cupertino, CA) Quick Board application and a footpad with 5 sensors placed equidistant from each other, with two at the front of the footpad, two at the back of the footpad, and one in the middle of the footpad. Upper and lower body reaction time will be measured using hands and legs, respectively. Prompts will be displayed by the iPad software to instruct the participant with quick time tasks.
- 9. After Day 1, participants will be instructed to restrict their sleep to 50% of their habitual sleeping duration. The goal is to provide a consistent start-and-stop sleep schedule:
 - a. Example 1: if a participant sleeps on average 6 hours per night, then 50% reduction will result in 3 hours per night for 4 nights in a row. A target sleeping schedule will be from 3am 6am.
 - b. Example 2: if a participant sleeps on average 8 hours per night, then 50% reduction will result in 4 hours per night for 4 nights in a row. A target sleeping schedule will be from 3am 7am.
- 10. After testing on Day 5 (i.e. after 4 nights of consecutive sleep restriction) the participants can resume regular sleeping habits for two weeks until they return to the lab to begin their second cross-over condition.

Day 2, 3, & 4:

- 1. Participants will be asked to maintain normal training schedule during these days.
- 2. The goal is to make sure that training during and between supplement condition remains same to control for confounding effects.
 - a. For example, if a participant must run and train for ROTC duties Tuesday, Wednesday, Thursday (e.g. Days 2, 3, 4) then he/she will be asked to record the training regimen in the training log and closely replicate the same exercises (intensity and duration) throughout the study.

Privacy.

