The consent room (PAES A023) will be used as the private consenting location. For all the data collected over the course of the study (i.e. records, biological samples and questionnaires) each participant will receive a unique subject identifier (i.e. a code) instead of using their legal name. Each unique identifier will only be available to research personnel.

Confidentiality.

Prior to signing the informed consent form all participants will be informed that their participation in the study is voluntary and that they may withdraw at any time. Participants who provide written consent are considered enrolled in the study. All records or biological data obtained after signing of the informed consent (including the screening visit, even for subjects that are not eligible for participation in the study) are treated with the same confidentiality safety measures as those subjects who qualify. Any information obtained during the prescreening for participants that were not eligible will be deleted. Hard copy data storage will be stored away in a locked file cabinet. Digital data will be protected on a computer via password. Subject names will never be used in any presentation or publication resulting from this study. The records will be maintained until the data are published and up to a maximum of ten years after the completion of the study.

Sleep Deprivation Disclaimer

According to the National Institute of Health, sleep deprivation is known to affect driving safety. Participants who undergo study-supervised sleep restriction are prone to falling asleep when stopped at a light and while driving. This situation increases the likelihood of motor vehicle accidents and traffic law violations, respectively. To avoid these risks we plan to collaborate with OSU-approved ride services (i.e., Lyft) to provide transportation for participants who commute to campus via car. 100% of the cost will be re-imbursed using university accepted PCards or check.

Withdrawal from the Study.

Participants may be removed from the study for any of the following reasons:

- Discontinuation request;
- Medical or compliance reasons;
- Occurrence of any adverse event or condition that could, in the investigator's opinion, interfere with the evaluation of the effect of the study methods or put the participant at undue risk.

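### The protocol names falling asleep at the wheel as a consequence of its sleep restriction, but its only stated measure is rides for participants who travel to campus by car

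*Protocol*

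**What the plan says.** The Sleep Deprivation Disclaimer states the hazard in general terms: "Participants who undergo study-supervised sleep restriction are prone to falling asleep when stopped at a light and while driving". It links this to a higher chance of accidents and traffic violations. The response follows directly: "To avoid these risks we plan to collaborate with OSU-approved ride services", in order to "provide transportation for participants who commute to campus via car", at full reimbursement. Participant Compensation adds that the team pays outside costs arising from the study, with transport as the example.

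The restriction itself is set out under Research Objective, Sleep Outcomes: "Participants will be required to reduce sleep by 50% of normal, for 4 consecutive nights". Test Day 1 & 5, item 9, starts it after Day 1 and gives worked examples; for a habitual 8-hour sleeper, "then 50% reduction will result in 4 hours per night for 4 nights in a row". Item 10 ends it after Day 5 testing, when "the participants can resume regular sleeping habits for two weeks until they return to the lab". The whole sequence is repeated in the second period after a two-week washout.

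**The concern.** The hazard covers driving of every kind, whereas the measure covers participants who drive to campus and, on its natural reading, their campus trips. Errands, work, family journeys, and driving later on Day 5 before any recovery sleep are left unaddressed by this section. A participant who walks to campus but drives elsewhere gains nothing from it.

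The study procedure creates the hazard, and the possible harm extends to other road users. The Background also cites a marksmanship study in which sleep-restricted subjects performed worse but did not perceive a change. On the protocol's own evidence, participants' judgement of their own fitness to drive is not a dependable safeguard, which is a reason for an explicit instruction.

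**Working it through.** The protocol gives no figure to reproduce, and the point depends on no statistical quantity. The check compares the relevant sections and counts the days concerned.

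**1. Risk against measure (Sleep Deprivation Disclaimer)**
- Risk: any driving while sleep-restricted.
- Measure: planned rides for those who travel to campus by car. Their use is not made compulsory.

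**2. What the rides plausibly cover**
- Testing Sessions has a familiarization meeting "followed by 5, consecutive, in-person testing sessions".
- Exercise Performance says "All physical activity will be performed in our laboratory weight room".
- For participants who would otherwise drive in, the rides can reasonably be taken to cover these trips, including the journey home after Day 5 testing.
- The boundary is not sharp. The Day 2, 3, & 4 section asks participants to keep their normal training and uses ROTC duties as its example, so some training travel may fall outside the rides.

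**3. Search for any other driving instruction**
- Sleep Outcomes, Exercise Performance, Experimental Approach, Familiarization, Test Day 1 & 5, and Day 2, 3, & 4: none.
- Participants (eligibility): no exclusion of people who must drive.
- Withdrawal from the Study: a general undue-risk criterion, which is not a driving rule.
- Participant Compensation: study-related costs only.

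**4. Days concerned**
- Sleep Outcomes and Test Day 1 & 5: 4 restricted nights, the first after Day 1, so the affected days are Days 2 to 5, which is 4 days per period. Over two periods: 4 × 2 = 8 days.
- Experimental Approach, read literally, restricts the night of Day 1 and four more: 1 + 4 = 5 nights, so Days 2 to 6, which is 5 days per period. Over two periods: 5 × 2 = 10 days.

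These are days under restriction. The protocol gives no driving time, so the uncovered share of driving cannot be calculated.

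**The case against.** The strongest objection is that a driving warning is an instruction to participants, and the consent form is its usual home. Those pages were removed from the supplied text. Screening says the study is described in full during consent, and Participants says volunteers are familiarized with the research beforehand. A reader might infer from the protocol that participants are never told to avoid driving. The documents do not support that, because the likeliest place for such an instruction was not seen. What stands is narrower: the Disclaimer itself pairs a general risk with a limited measure.

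Second, the rides address the travel that the study generates, and how far a protocol should govern personal travel is for the investigator and the IRB. That is fair. The protocol carries an IRB approval date, but approval does not settle whether this wording is adequate, and the section presents the rides as its answer to the whole risk.

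Third, the sentence identifies who receives transport and does not list eligible trips. Campus travel is still the more natural reading.

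Fourth, a reader might use the size of the sleep loss to size the gap. In the item 9 examples the loss by Day 5 is 3 × 4 = 12 hours for a 6-hour sleeper and 4 × 4 = 16 hours for an 8-hour sleeper. Those figures describe the intervention and say nothing about how much driving is uncovered.

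**Conclusion.** The point holds as a limited one. The protocol names a driving hazard caused by its own procedure, and the only measure it states does not reach driving other than to campus while participants are sleep-restricted. The period is 4 days per treatment period on the four-night schedule, or 5 on the literal five-night reading.

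The conclusion assumes that the rides are meant for campus travel and that nothing in the unseen consent pages is being contradicted. If the consent form already forbids driving, all that remains is to bring the protocol text into line with it.

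A reader might also infer that the sponsor must pay for personal journeys. The documents do not establish that; it is a question of resources and no part of this point. There is no effect on bias, power or analysis.

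**What to change.** Add to the Sleep Deprivation Disclaimer that participants are instructed not to drive from the morning after the first restricted night until after at least one unrestricted night of sleep following the last restricted night, in both periods. Give the instruction at familiarization and on Day 1 of each period. Keep the existing rides. If the consent form already contains a driving instruction, match its wording.

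Tying the rule to the first and last restricted nights, and not to day numbers, means it works under either night count. The documents do not show that one unrestricted night is enough to drive safely. It is a proposed minimum, and the investigator may set a longer interval.

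The cost is a short text amendment and a reminder at visits that already take place. The downside is inconvenience on about 4 days per period (5 on the longer reading) for participants who need to drive, which might deter a few from enrolling.

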a) Continuous quantification of interstitial fluid glucose and beta-hydroxybutyrate (BHB) will be monitored using sensor-based devices developed and manufactured by Abbott Biowearables. The systems consist of three components: 1) a sensor that incorporates a subcutaneously implanted electrochemical glucose/ketone sensor and associated on-body electronics. 2) a disposable, sensor application device, which is used to adhere the sensor to the skin of the user and to insert the sensor tail just below the surface of the skin. And 3) a handheld device (reader or phone app) which activates the sensor by near-field communication and continuously obtains glucose and BHB readings at one-minute intervals from the sensor via Bluetooth short-range wireless communication. A separate sensor will be used for glucose and BHB monitoring. Sensor values will be blinded to the participant and research personnel such that the reader (or phone) only displays whether or not the matching sensor is functional or not. Glucose and BHB sensor data is therefore not accessible for medical or non-medical decision-making. Readers (or Phones), sensors, and Patch Delivery Units are uniquely identifiable through individual serial numbers. Readers (or Phones) require periodic charging

with a power chord (at least weekly). Sensors do not require charging. The wear period for a sensor is 14-days and thus we will have participants apply new sensors during the second cross-over period after the 14-day washout period. Sensors will be placed on the non-dominant arm (mid-triceps region) during each experimental phase.

b) Fasting venous blood will be collected at baseline and on Day 1 and Day 5 of the sleep restriction protocol to measure metabolites and hormones in serum and plasma. Participants will be exposed to a maximum of 4 blood draws during the entire study.

METHODS

Experimental Approach.

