We will conduct a double-blind, placebo-controlled, two-period cross-over study (**Figure 1**). The order of treatment will be balanced (i.e., half start with KE and half start with Placebo). Participants (n = 60) will be familiarized with all the physical performance tests to minimize learning effects and undergo baseline assessments. Subjects will then be randomized to either the KE or Placebo condition. On the morning of Day 1, prior to administration of KE or Placebo, subjects will undergo Pre-Testing inclusive of a blood draw, physical, and cognitive performance. For that night, and the next 4 nights, all subjects will restrict their sleep by 50%. On the morning of Day 5, the same testing battery performed on Day 1 will be replicated. KE or Placebo ingestion will occur on Days 2, 3, and 4 (2 doses/day), and include 1 dose on Day 5. After a 2-wk washout period, during which time participants return to their normal sleep and exercise habits, they will replicate the exact same 5-day protocol except they will receive the opposite treatment.

[figure not shown]

Figure 1 | Experimental Design

Rationale for Design.

We expect to show that short-term sleep restriction combined with physical exertion is associated with disturbed glucose metabolism as well as impaired cognitive function and physical performance. Based on emerging animal and human evidence indicating that ketosis is associated with enhanced cognition and improved physiological tolerance and performance in response to physical exertion [25, 26], our central **hypothesis** is that KE ingestion will lessen the detrimental effects of sleep restriction on cognitive and physical performance. This will be the first work to specifically explore how ketosis impacts cognition in the context of sleep restriction and performance tasks.

Participants.

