It is understood by all concerned that an excessive rate of withdrawals can render the study uninterpretable, therefore, unnecessary withdrawal of participants should be avoided. Should a participant decide to withdraw, all efforts will be made to complete and report observations as thoroughly as possible and documented in the eCRF.

Serious Adverse Event Reporting Instructions.

If in the opinion of the Investigator the event meets the criteria of a SAE the following procedures will be followed:

- The Investigator will notify Institutional Review Board (IRB) of the SAE within the parameters and timeframe specified under the IRB Standard Operating Procedures (SOP). An initial report followed promptly by a complete report will be forwarded to the IRB, when applicable.
- If a participant is hospitalized or hospitalization is prolonged due to the SAE, the hospital discharge summary will be obtained if possible.
- If a death occurs and an autopsy is performed, a copy of the autopsy report will be obtained if possible.
- All efforts must be undertaken to obtain follow-up information promptly.

Recording of Adverse Events.

All AEs (AE or SAE) will be recorded on the AE study documents. For participants who have an ongoing AE at their final study visit, follow-up information will be captured in the AE eCRF page which will be completed after 30 days.

Serious Adverse Event Follow-Up.

For all ongoing SAEs occurring during the study, the Investigator must submit follow-up reports regarding the participant's subsequent course. All SAEs that are ongoing at the end of the study or upon discontinuation of the participant's participation must be followed until either:

- The event resolves, or
- The event/condition has stabilized (e.g., in the case of persistent impairment), or
- The event returns to baseline, if a baseline value is available, or
- The participant dies, or
- The event can be attributed to other than the study beverage, or to other than the study conduct.

Participant Compensation.

Participants who complete all study duties will be compensated with a \$300 PCard or a check. No compensation will be provided for completing the screening visit. Payments will be prorated by condition: each 5-day condition will result in \$150; completion of both conditions (KE and Placebo) will result in \$300. Any external costs associated with the study (i.e., transportation) will be covered by the study team.

Data analysis.

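### No contact is scheduled after the last visit for a participant without an ongoing adverse event, so later events are recorded only if volunteered

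*Protocol*

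**What the plan says.** Under Recording of Adverse Events the protocol makes a general promise: "All AEs (AE or SAE) will be recorded on the AE study documents". It gives no start or end of the collection period and no occasion on which participants are asked. The next sentence holds the only AE step after the last visit: "For participants who have an ongoing AE at their final study visit, follow-up information will be captured in the AE eCRF page". The same sentence sets the time for that form at 30 days.

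Serious Adverse Event Follow-Up is restricted in the same way: "All SAEs that are ongoing at the end of the study or upon discontinuation of the participant's participation must be followed until either" one of the listed outcomes is reached.

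The last visit is Day 5 of the second period. On dosing, Experimental Approach says: "KE or Placebo ingestion will occur on Days 2, 3, and 4 (2 doses/day), and include 1 dose on Day 5". The steps for Test Day 1 & 5 place the dose ahead of the cognitive battery. They end with release: "After testing on Day 5 (i.e. after 4 nights of consecutive sleep restriction) the participants can resume regular sleeping habits". Neither the study procedures nor Table 1 shows a visit or call after that day in the second period.

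The Sleep Deprivation Disclaimer names falling asleep at the wheel, and the resulting motor vehicle accidents, as a risk of the restriction. It offers paid rides to participants who commute to campus by car.

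**The concern.** Post-study follow-up depends on an event being present at the last visit. It tracks problems already known and does not look for new ones. The last visit comes when the accumulated sleep loss is at its largest under the four-night schedule, and on a day on which a dose has been taken. A participant could leave well and have an accident, a fall or a gastrointestinal complaint later that day or night, and nobody would be due to ask.

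What is at stake is the completeness of the safety record. The trial deliberately exposes healthy volunteers to a hazard that it names in advance. A count of harms that depends on volunteered reports after the final exposure is likely to be too low by an amount that cannot be estimated afterwards.

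**Working it through.** The plan states no figure on this point, so there is none to reproduce. The check is a reading of the sections side by side, with two small calculations.

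**1. Who is contacted after the last visit?**
- AE ongoing at the last visit: followed, with the form completed after 30 days (Recording of Adverse Events).
- SAE ongoing at study end or discontinuation: followed to resolution, stabilisation or another listed outcome (Serious Adverse Event Follow-Up).
- No ongoing event: no contact is stated anywhere.
- Early withdrawal without an ongoing event: Withdrawal from the Study asks for observations to be completed as fully as possible, but schedules no later contact.

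**2. Sleep loss at the last visit.** Inputs are the two examples under Test Day 1 & 5. Cumulative loss on the morning of day d = (d − 1) × 0.5 × habitual hours.

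| Habitual sleep | Day 1 | Day 2 | Day 3 | Day 4 | Day 5 |
|---|---|---|---|---|---|
| 6 h | 0 | 3 | 6 | 9 | 12 h |
| 8 h | 0 | 4 | 8 | 12 | 16 h |

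The loss is largest on Day 5, the day of release.

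Experimental Approach counts differently: the night of Day 1 plus four more, which read literally is five nights. Sleep Outcomes and the Test Day steps give four. A fifth night would fall after Day 5 testing, and the loss would reach 5 × 3 = 15 h or 5 × 4 = 20 h after the last visit, inside the window without contact. These sections must be reconciled.

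**3. Dose and release.** Supplementation gives about 5 hours of ketosis per dose. The dose comes before the cognitive tests, surveys, shooting, jump and reaction tests. Visit length is not stated, so part of the 5 hours is observed and some may run past release; how much is unknown.

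**4. How many windows?** Each completer leaves after two Day 5 visits. After the first, the participant returns about two weeks later for Day 1 of the second period, so there is an occasion to report, although the protocol does not say that anyone asks. After the second there is no later occasion. With 60 enrolled, the number of final windows without a scheduled contact is at most 60 × 1 = 60, less those with an AE ongoing at that visit.

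**5. Days 2 to 4.** Testing Sessions describes familiarization "followed by 5, consecutive, in-person testing sessions". Exercise Performance places weight-training workouts on these days, supervised and in the laboratory. The Day 2, 3, & 4 steps instead have participants keep their normal training and log it. Table 1 lists only heart-rate and sensor recording on these days. The sections disagree on whether staff see participants then, and must be reconciled.

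**The case against.** **Later events are not excluded.** The general promise to record all AEs has no end date, and the conditional sentence governs how known events are followed, not which onsets count. A reader might infer that events starting after release are not collected. The documents do not support that: a volunteered report could be entered. The AE forms are not at hand and the consent pages were removed, so what participants are told about reporting cannot be seen. This stands, and it limits the point to the absence of a scheduled contact.

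**Half of all windows.** A reader might count 120 post-Day-5 windows (60 × 2) and call half of them uncollected. That is inconsistent: no AE question is stated at the second-period return visit either, so the first-period windows cannot be credited as collected. Nor do windows count events, and no event rate is given.

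**Days 2 to 4.** A reader might infer from Table 1 that staff contact is absent on these days. It does not follow. The table is a checklist of measurements and also omits dosing and workouts, while other sections describe in-person sessions and supervised exercise. Of the sensor readings the protocol says: "Glucose and BHB sensor data is therefore not accessible for medical or non-medical decision-making". That is deliberate blinding and does not stop a participant reporting symptoms. What remains is a contradiction to resolve.

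**The risk is mitigated.** Part of the post-dose period is observed, paid rides are offered, and Supplementation cites good tolerability. All true. But the rides are for participants who commute to campus by car, do not cover other driving, and collect no events.

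**No bias between treatments.** Treatment order is balanced, so about 30 of 60 final windows would follow each product. This stands: the weakness is incomplete ascertainment, and no bias in favour of either product is shown.

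**The statistical analysis plan is not shown.** That plan would govern how AEs are analysed. Whom to contact, and when, is protocol content, and here the protocol fixes it too narrowly.

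**Conclusion.** The point holds in a limited form and should be acted on. Followed exactly, the protocol schedules no contact after Day 5 of the second period for a participant without an ongoing event. That is when accumulated sleep loss is 12 to 16 hours on the protocol's examples and its named driving hazard may still apply. Up to 60 completers are affected, and early withdrawals without an ongoing event are in the same position. The number of events missed is unknown and may be small.

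The conclusion assumes that no unseen form or consent text already sets a final contact. It also takes the four-night schedule; on the five-night reading the gap would be larger. It does not rest on any claim about Days 2 to 4.

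**What to change.** - Under Recording of Adverse Events, extend the existing 30-day follow-up to all participants, including early withdrawals, and ask about new events since the last visit as well as the course of ongoing ones.
- At Day 1 of the second period, an existing visit, ask about events since Day 5 of the first.
- Separately, reconcile the description of Days 2 to 4 (Exercise Performance and Testing Sessions against the Day 2, 3, & 4 steps) and the number of restricted nights (Experimental Approach against Sleep Outcomes and the Test Day 1 & 5 steps).

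The cost is a short amendment and about 60 brief calls or messages by existing staff, one per participant, fewer where follow-up of an ongoing event is already due. No new procedure is needed, and dosing and the sample size are unaffected.
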